9.2 Statistical Analysis

Complete details of the statistical analysis will be provided in the Statistical Analysis Plan (SAP). Any deviations from, or additions to, the original analysis plan described in this protocol will be documented in the SAP and final study report.

When determining the RP2D, the totality of the safety, tolerability, PK, PD, and efficacy data collected during both dose escalation and dose expansion is taken into consideration.

9.2.1 Analysis Populations

The populations defined for analysis will include the following:

Population	Description
Screened	All subjects who have signed the main study ICF
Screen Failures	All subjects who have signed the main study ICF but have not received any study treatment.
All Treated	All subjects who receive at least one dose of SL-172154, PLD, or MIRV. Safety data will be evaluated based on this population.

Population	Description
DLT-Evaluable	All subjects enrolled in the dose escalation cohorts who receive at least 50% of the scheduled doses of SL-172154 and 1 dose of PLD or MIRV and complete the safety follow-up through the DLT evaluation period or experience any DLT during the DLT evaluation period. DLT-evaluable subjects will be used to guide dose escalation and to determine the MTD or MAD.
Response-Evaluable	Subjects in the All Treated Population who have either had at least one post-baseline disease assessment or who have discontinued study treatment due to disease progression or death before any post-baseline disease assessment.
Pharmacokinetic	Subjects in All Treated Population from whom at least one post-baseline PK sample is obtained and analyzed
Pharmacodynamic	Subjects in the All Treated Population for whom a baseline and at least one on-treatment PD sample is obtained and analyzed.

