The safety evaluation for each combination regimen will be based on the All-Treated Population defined as all subjects who received at least one dose of study treatment. Frequency tables by dose levels will be used to describe safety and tolerability parameters such as: AEs, SAEs, fatal AEs, and AEs leading to discontinuation of SL-172154, PLD or MIRV. Changes in toxicity grade for laboratory parameters will also be summarized. AEs will be mapped to a Medical Dictionary for Regulatory Activities (MedDRA) preferred term and system organ classification. All AEs except CRS and ocular AEs will be graded according to the NCI CTCAE v5.0. CRS will be graded per the ASTCT Consensus Grading Criteria for CRS; ocular AEs for the MIRV cohort will be graded per the tables provided in the Appendix. The DLT evaluation will be based on the DLT-evaluable population. The DLT-evaluable population for SL-172154 + PLD and SL-172154 + MIRV is defined as all subjects enrolled in the dose escalation cohorts who receive at least 50% scheduled doses of SL-172154 and one dose of PLD or MIRV and complete the post-treatment visit (PTV) through the DLT evaluation period or experience any DLT during the DLT evaluation period. DLTs will be summarized by dose level for each of the combination dose escalation cohorts. The MTD will be estimated using isotonic regression. Continuous toxicity monitoring based on the Pocock-type stopping boundary [Ivanova, 2005] will be used for the rate of AEs leading to treatment discontinuation within each of the dose expansion cohorts.

Anti-tumor activity data will be summarized by dose level and for all subjects for each combination regimen, respectively, in the All Treated population and Response-Evaluable population (defined as Subjects in the All Treated Population who have a baseline disease assessment and have at least one post-baseline disease assessment or have progressed or died before the first post-baseline disease assessment). The ORR and CBR based on investigator-assessed response per RECIST v1.1 will be estimated along with a 95% confidence interval using the exact probability method. Duration of response and time to response will be evaluated, using the Kaplan-Meier method, for the subgroup of

subjects with a confirmed response. The Kaplan-Meier method will be used to estimate the PFS/OS curve and PFS/OS rate at timepoints of interest.

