3.2.1 SL-172154 Administered with Pegylated Liposomal Doxorubicin (PLD)

SL-172154 (3.0 mg/kg starting dose) will be administered by IV infusion on Days 8 and 15 of each 28-day cycle. Premedication as prophylaxis for IRR with dexamethasone (8 mg IV), an antipyretic and antihistamines should be administered at least 30 minutes prior to each SL-172154 administration as described in Section 5.1.1. PLD (40 mg/m², IV) will be administered on Day 1 of each 28-day cycle. Administer the first dose (Cycle 1 Day 1) of PLD as a 1 mg/min infusion; after Cycle 1, if tolerated, PLD can be delivered as a 1-hour infusion. Premedication (any agent except steroid) as prophylaxis for nausea and vomiting with PLD may be administered per institutional guidelines.

The planned dose escalation of SL-172154 is outlined in Table 1; additional doses and/or schedules may be explored based on emerging safety, PK and PD data. SL-172154 doses explored in SL03-OHD-105 will not exceed the highest dose determined to be safe and tolerable in the monotherapy dose escalation study SL03-OHD-101.

Subjects will be enrolled in cohorts of approximately 3 subjects into sequential dose levels of SL-172154 administered with PLD and evaluated for DLT during the 28-day DLT evaluation period. DLT criteria are defined in Section 3.5. Treatment will be administered in 28-day cycles until at least one of the study treatment discontinuation criteria is met (Section 3.1.1). During therapy, management of PLD-related toxicity should follow the guidelines provided in the current PLD label, or local guidelines and are described in Section 3.7.2. Subjects will be followed according to the Schedule of Assessments (SOA) in Section 6.1.

The safety as well as available PK, PD, and efficacy data from these subjects will inform the dose of SL-172154 selected to be further evaluated in dose expansion when administered in combination with PLD to subjects with platinum-resistant ovarian, primary peritoneal, or fallopian tube cancer.

Table 1 SL-172154 Dose Escalation Plan When Administered with PLD

Dose Level ^a	SL-172154 Dose ^b [D8 and 15 in each 28d cycle]	SL-172154 Infusion ^c	Pegylated liposomal doxorubicin (PLD)
-1 ^d	1.0 mg/kg	60 min \pm 10 min	PLD (40 mg/m ²) IV administered on Day 1 of each 28-day cycle Administer first dose on study (C1D1) as 1 mg/min IV infusion; after Cycle 1, if tolerated, PLD can be delivered as a 1-hour infusion
1 (Starting Dose)	3.0 mg/kg	120 min \pm 15 min	

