3.2.2 SL-172154 Administered with Mirvetuximab Soravtansine (MIRV)

SL-172154 (3.0 mg/kg starting dose) will be administered by IV infusion on Day 8 and Day 15 of 21-day cycles. Premedication as prophylaxis for IRR with dexamethasone (8 mg IV), an antipyretic and antihistamines should be administered at least 30 minutes prior to each SL-172154 administration as described in Section 5.1.1. MIRV (6.0 mg/kg AIBW, IV) will be administered on Day 1 of each 21-day cycle. Premedication with antipyretic, antihistamine, and dexamethasone will be administered at least 30 minutes prior to each MIRV administration as described in Section 5.3.2.1. Prophylactic use of eye drops with MIRV administration is described in Section 5.3.2.2.

The planned dose escalation of SL-172154 is outlined in [Table 2](#); additional doses and/or schedules or intermediate doses may be explored based on emerging safety, PK, and PD data. SL-172154 doses explored in SL03-OHD-105 will not exceed the highest dose determined to be safe and tolerable in the monotherapy dose escalation study SL03-OHD-101.

Subjects will be enrolled in cohorts of approximately 3 subjects into sequential dose levels of SL-172154 administered with MIRV and evaluated for DLT during the 21-day DLT evaluation period. DLT criteria are defined in Section 3.5. Treatment will be administered in 21-day cycles until at least one of the study treatment discontinuation criteria is met (Section 3.1.1). During therapy, management of MIRV-related toxicity should follow the guidelines provided in Section 3.7.3 and the MIRV IB or the current USPI, as applicable. Subjects will be followed according to the SOA in Section 6.2.

The safety as well as available PK, PD, and efficacy data from these subjects will inform the dose of SL-172154 selected to be further evaluated in dose expansion when administered in combination with MIRV to subjects with platinum-resistant ovarian, primary peritoneal, or fallopian tube cancer.

Table 2 SL-172154 Dose Escalation Plan When Administered with MIRV

Dose Level ^a	SL-172154 Dose ^b [D8 and D15 in each 21d cycle]	SL-172154 Infusion ^c	Mirvetuximab soravtansine (MIRV) ^e
-1 ^d	1.0 mg/kg	60 min ± 10 min	6.0 mg/kg AIBW, IV administered on Day 1 of each 21-day cycle

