3.5 Definition of Dose-Limiting Toxicity

Protocol-defined DLT criteria are applicable to the dose escalation portion of the study. The determinant period for DLT is the first cycle of treatment (i.e., 28 days for PLD cohorts, 21 days for MIRV cohorts); however, there is provision in the criteria below for AEs that occur beyond this period to be considered in the determination of the RP2D. All toxicities except for CRS and ocular AEs will be graded as per NCI CTCAE v5. CRS will be graded per the American Society for Transplantation and Cellular Therapy (ASTCT) Consensus Grading Criteria for CRS (described in Section 3.7.1.2); ocular AEs for the MIRV cohort will be graded per the tables provided in the Appendix Section 16.6. AEs clearly related to the underlying disease, disease progression, intercurrent illness, or concomitant medications are not considered DLTs. AEs that are clearly related to PLD or MIRV only do not have to be considered DLTs, unless the investigator considers the AE to be exacerbated by SL-172154. DLT is defined as an event considered related or possibly related to SL-172154 and meets one of the following criteria:

- Any death not clearly related to underlying disease or intercurrent illness
- Elevations in liver transaminases (aspartate aminotransferase [AST], alanine aminotransferase [ALT]) or total bilirubin:
 - In subject who enroll with AST/ALT/total bilirubin \leq upper limit of normal (ULN), AST or ALT elevation of $> 8x$ ULN **or** total bilirubin $> 5x$ ULN.
 - In subjects who enroll with AST/ALT/total bilirubin $>$ ULN, AST or ALT elevation of $> 8x$ baseline **or** total bilirubin $> 5x$ baseline.
 - Evidence of Hy's Law (AST or ALT $> 3x$ ULN [or baseline*] with concurrent increase in total bilirubin $> 2x$ ULN [*or baseline] without evidence of cholestasis or alternative explanation such as disease progression or viral hepatitis.

**ULN or baseline dependent on value at enrollment as described above.*

- Any AE that requires permanent discontinuation of SL-172154
- Any Grade 3 or greater AE except for those listed below:
 - Grade 3 fatigue lasting ≤ 7 days
 - Grade 3 anemia
 - Grade 3 or 4 neutropenia not associated with fever (temperature $> 38.5^{\circ}\text{C}$) that improves to Grade 2 within 7 days
 - Grade 3 or 4 lymphopenia
 - Grade 3 thrombocytopenia not associated with clinically significant bleeding and does not require medical intervention

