Grade 2	
• Temporarily interrupt SL-172154.• Vital signs should be measured after the onset of an IRR approximately every 15 minutes through the completion of the infusion followed by approximately every 15 minutes for one hour after completion of the SL-172154 infusion and then approximately every 30 minutes for the second hour after the completion of the SL-172154 infusion.• Begin IV infusion of normal saline and treat symptoms as indicated and per institutional guidelines, e.g., with antipyretic and antihistamines; consider opioids (e.g., meperidine) for rigors, leukotriene inhibitor, bronchodilator therapy, or corticosteroids as appropriate.• Monitor subjects with close observation in an outpatient or inpatient setting until recovery from symptoms. Consider if admission to hospital is necessary.

General Guidance for Infusion-Related Reactions (IRRs) [Rosello, 2017a]	
	
• Restart the infusion after resolution of symptoms. Based on the severity of symptoms, reduce the rate to $\leq 50\%$ of the rate at which the reaction occurred.• If symptoms recur, then no further SL-172154 will be administered at this visit.• Subsequent Infusions:
◦ If the Grade 2 IRR signs and symptoms were not severe, the investigator may administer the next two infusions at the current dose but at $\leq 50\%$ rate. If the symptoms do not recur, the infusion rate may be increased back to the original rate stated in the protocol.◦ If the Grade 2 IRR signs and symptoms were severe, the investigator may reduce the SL-172154 dose for the next two infusions to 1 mg/kg. If the symptoms do not recur, SL-172154 dose may be increased back to 3 mg/kg at $\leq 50\%$ of the original rate. If tolerated, the rate may be increased back to the original rate stated in the protocol.
Recurrent Grade 2	
• If the Grade 2 IRR recurred after reducing the dose to 1 mg/kg and the signs and symptoms are severe, permanently discontinue SL-172154

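### DLT evaluability is set by the number of SL-172154 doses, not the amount delivered, so an under-exposed DLT-free subject can count as a full non-event at the assigned dose level

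*Protocol*

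**What the plan says.** Protocol 9.2.1 and SAP 4 use the same rule, which opens "All subjects enrolled in the dose escalation cohorts who receive at least 50% of the scheduled doses of SL-172154 and 1 dose of PLD or" and goes on to name MIRV as the other partner drug; these subjects must then either complete safety follow-up through the DLT window or have a DLT in it. Both sections make this the population that guides escalation and fixes the MTD or MAD.

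The window is Cycle 1 (Protocol 3.5): "The determinant period for DLT is the first cycle of treatment (i.e., 28 days for PLD cohorts, 21 days for MIRV cohorts". In the PLD cohorts SL-172154 "will be administered by IV infusion on Days 8 and 15 of each 28-day cycle" (3.2.1); in the MIRV cohorts it "will be administered by IV infusion on Day 8 and Day 15 of 21-day cycles" (3.2.2). Either way, two doses are scheduled in the window.

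The management guidance allows a Cycle 1 dose to be cut short, reduced or omitted for events below Grade 3:
- After a Grade 2 infusion-related reaction (IRR) and a restart (3.7.1.1): "If symptoms recur, then no further SL-172154 will be administered at this visit".
- After a severe Grade 2 IRR, "the investigator may reduce the SL-172154 dose for the next two infusions to 1 mg/kg" (3.7.1.1).
- A dose not given is treated as skipped (3.7), and a Grade 2 ALT/AST rise not resolved within 7 days leads to a held or skipped dose (3.7.1.3).

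SAP 8.1.2 derives the mg actually received and a relative dose intensity, but only for the exposure summary. The Protocol Synopsis (Statistics) words the follow-up condition differently: subjects must "complete the post-treatment visit (PTV) through the DLT evaluation period".

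**The concern.** A DLT rate at a dose level means something only if the subjects in the denominator were exposed to roughly that dose. Here the denominator is defined by a count of doses. The term for a dose received is not defined, and SAP 8.1.2 summarises the number of doses received separately from infusions not completed, so a stopped infusion can be counted as a dose.

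An under-exposed subject without a DLT then adds one to the denominator at the assigned level and nothing to the numerator. The mTPI-2 decisions and the isotonic MTD both use this denominator, so the error runs one way, toward escalation. Cohorts are of about three, so one such subject can change a decision.

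**Working it through.** **Delivered share at the 3 mg/kg level.** Planned Cycle 1 drug is 2 × 3 = 6 mg/kg. Assume, for illustration, that half of the Day 8 infusion (1.5 mg/kg) was given.
- Day 15 skipped: 1.5/6 = 25% of planned drug, counted as 1 of 2 doses.
- Day 15 at 1 mg/kg: (1.5 + 1)/6 = 42% of planned drug, counted as 2 of 2 doses.

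Both subjects meet the rule. The IRR guidance does not itself prescribe skipping the next dose, so the first case also needs one of the skip provisions in 3.7 or 3.7.1.3.

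**The plan's decision table.** I used a Beta(1 + x, 1 + n − x) posterior, subintervals of length 0.1 around (0.25, 0.35), the decision from the subinterval with the highest unit mass, and the unsafe flag when the posterior probability of a rate above 0.30 is at least 0.95. This reproduces SAP Table 3 in all 75 cells and Protocol Table 12 in 74. At 3 DLTs in 8 the protocol prints S; the model, the SAP and the protocol's own rule for rates above 33% give D.

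**What one subject does to the table.** Removing one DLT-free subject, with at least three left, changes 9 of 72 combinations of DLTs and subjects, always to a more cautious decision:
- E to S: 1/5 becomes 1/4; 2/9 becomes 2/8.
- S to D: 2/6 becomes 2/5; 3/9 becomes 3/8; 4/12 becomes 4/11.
- D to DU: 3/5, 4/7, 5/10 and 6/12.

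In a first cohort, 0/3 (escalate) becomes 0/2, below the required minimum of three evaluable subjects. The observed rate is 0% either way; the harm there is escalation on fewer than three adequately exposed subjects.

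**Effect on escalation.** The documents give neither the share u of under-exposed subjects nor their DLT risk r, so both are assumed. With a full-exposure risk of 0.35, the expected rate is q = 0.35(1 − u) + r·u, and the chance of 0/3 is (1 − q)³. With u = 0 this is 0.65³ = 0.275.

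| u | r = 0 | r = 0.10 | r = 0.175 |
|---|---|---|---|
| 11% | 0.326 | 0.311 | 0.300 |
| 21% | 0.379 | 0.347 | 0.324 |
| one third | 0.451 | 0.394 | 0.355 |

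For example, u = 11% and r = 0.10 give q = 0.89 × 0.35 + 0.11 × 0.10 = 0.3225 and 0.6775³ = 0.311. With u = one third, q = 0.267 and 0.733³ = 0.394.

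The 11% and 21% are one-sided 95% upper bounds. Protocol 1.7.1 reports that all 26 monotherapy subjects received their full scheduled dose: 1 − 0.05^(1/26) = 0.109. The 13 subjects treated at 3 or 10 mg/kg (2 + 6 + 5, Protocol 1.4.7) give 1 − 0.05^(1/13) = 0.206. The one-third share has no support in the documents.

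**Synopsis wording.** The post-treatment visit falls 30 ± 7 days after the last study treatment (footnotes to Protocol 6.1 and 6.2). After a last dose on Day 15 the earliest date is Day 15 + 23 = Day 38, beyond both windows unless it is brought forward because a new anticancer therapy is starting. A subject continuing treatment could not complete it in the window.

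**The case against.** The strongest case against is that the problem may hardly occur. In monotherapy 12 of 26 subjects (46%) had IRR interruptions, yet all received the full dose, at levels up to 10 mg/kg against a planned maximum of 6 mg/kg here. This trial also adds dexamethasone premedication and longer infusions. That stands: the frequency is unknown, and the interruption rate does not measure under-delivery, although a reader might infer that it does.

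The plan also has safeguards. A related or possibly related Grade 3 or higher IRR, or an AE requiring permanent discontinuation, is already a DLT (3.5). The investigator with the SMC may classify other toxicities as DLTs. The SMC reviews all available safety and PK data, and the sponsor may add escalation subjects (9.1.4). These narrow the gap, but they are either limited to more serious events or discretionary. None changes who is counted when a subject remains DLT-free.

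A reader might infer that the plan states that partial infusions count as doses. It does not. The term is undefined, and counting them is the literal reading. A reader might also take the Synopsis wording as further evidence of the bias. It is a separate inconsistency: it would restrict the population rather than admit under-exposed subjects, and 9.2.1 and SAP 4 already refer to safety follow-up.

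**Conclusion.** The gap is real and its direction is clear: the rule sets no minimum amount and does not tie exposure to the assigned level, so under-exposed DLT-free subjects can pull the DLT rate down. Its size is not established. Under the assumed 35% and 10% DLT risks, the chance of escalating from a first cohort moves from 27% to about 31% at an 11% share, and to 39% only if one third of subjects are under-exposed. The documents do not support a claim that under-dosing was common or that escalation decisions were in fact wrong. The definition should be tightened because one subject can change a decision and the mg data are already derived.

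**What to change.** In Protocol 9.2.1, the Synopsis and SAP 4, keep the 50% figure but apply it to drug: at least 50% of the planned Cycle 1 SL-172154 mg at the assigned dose level, with actual mg as in SAP 8.1.2, or any DLT regardless of exposure. Keep the existing PLD or MIRV and follow-up conditions.

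Do not add a requirement for one complete infusion at the assigned level. One full infusion is already 3/6 = 50%, so the mg test would become redundant, and a subject with two infusions each 90% delivered would be excluded.

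DLT-free subjects below the threshold are left out of the decision table and replaced. They stay in the All Treated safety summaries and are listed with delivered dose at the dose meeting.

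Separately, replace the post-treatment visit in the Synopsis with safety follow-up, and reconcile the 3/8 cell between Protocol Table 12 and SAP Table 3, since 3/9 becomes 3/8 when one subject is set aside.

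The cost is wording, a per-subject mg check at each dose meeting and an occasional replacement. Replacement also selects somewhat toward subjects who tolerate infusions, which is why those set aside should be shown at the meeting. No dosing or IRR management rule changes.

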9.2.2 Data Analysis During Dose Escalation

During the dose escalation, the number of subjects with DLTs will be determined after each cohort of approximately 3 subjects has been evaluated for DLT. The summary of DLTs will be based on the DLT-Evaluable Population; the number of subjects with DLTs will be summarized by dose level for each of the combination dose escalation cohorts. Selected AE summary tables and listings may be provided during dose escalation to support dose escalation decisions.

9.2.3 General Data Analysis Consideration

Tabular summaries will be presented by dose levels/cohorts and total number of subjects in each of the combination regimens. Categorical data will be summarized by the number and percentage of subjects in each category. Continuous variables will be summarized by descriptive statistics.

As it is anticipated that accrual will be spread across centers and summaries of data by center would be unlikely to provide valuable information, data from all participating centers will be pooled prior to analysis. All data up to the time of study completion/withdrawal from study will be included in the analysis for each subject, regardless of duration of treatment.

9.2.4 Safety Analyses

The safety evaluation for each combination regimen will be based on the All-Treated Population and the DLT evaluation will be based on the DLT-evaluable population.

DLTs will be summarized by dose level/regimen for combination dose escalation cohorts. Frequency tables by dose levels will be used to describe safety and tolerability parameters such as: AEs, SAEs, fatal AEs and AEs leading to discontinuation of SL-172154, PLD or MIRV. Changes in toxicity grade for safety assessments (e.g., laboratory parameters, etc.) will also be summarized. Figures may also be presented where appropriate. AEs will be mapped to a Medical Dictionary for Regulatory Activities (MedDRA) preferred term and system organ classification. Concomitant medications will be coded using the World Health Organization Drug Dictionary. All toxicities except CRS and ocular AEs will be graded according to the NCI CTCAE v5.0. CRS will be graded per the ASTCT Consensus Grading Criteria for CRS (described in

Section 3.7.1.2); ocular AEs for the MIRV cohort will be graded per the tables provided in Appendix Section 16.6.

Maximum Tolerated Dose:

The MTD will be estimated using isotonic regression (based on the DLTs observed in DLT-evaluable subjects). Specifically, the MTD is the dose for which the isotonic estimate of the DLT rate is closest to the target DLT rate of 30% among all dose with the isotonic estimate of DLT rate $\geq 25\%$. If two or more doses tie for the smallest difference, the following rules will be performed:

- If the estimated DLT rate $< 30\%$ for all doses, then select the higher dose among the tied doses;
- If the estimated DLT rate for the tied doses are a combination of $< 30\%$ and $> 30\%$ for all doses, then select the higher dose among the tied doses;
- If the estimated DLT rate $> 30\%$ for all doses, then select the lower dose among the tied doses;

A Maximum Administered Dose (MAD) will be reported if the isotonic estimate of DLT rate is less than 25% for all dose levels. Otherwise, an MTD will be reported.

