9. STATISTICAL CONSIDERATIONS AND DATA ANALYSIS

9.1 Study Design and Sample Size Determinations

9.1.1 Dose Escalation

The SL-172154 dose escalation will utilize an mTPI-2 design [Guo, 2017] with a target DLT rate of 30% for the MTD.

The mTPI-2 design employs a simple Beta-Binomial Bayesian model with decision rules based on the unit probability mass from the posterior probability of DLT rate. With the target DLT rate of 30%, the posterior probability of DLT rate unit interval (0, 1) is divided into subintervals with equal length of 0.1 that correspond to different dose escalation decisions: subinterval of (0.25, 0.35) is to stay at the current dose, subintervals below 0.25 is to escalate to next higher dose, and subinterval above 0.35 is to de-escalate to the next lower dose. Subjects will be enrolled in cohorts of approximately 3 subjects during the dose escalation. After each cohort of approximately 3 subjects, the posterior unit probability for subintervals will be calculated based on a noninformative prior distribution for the DLT rate (Beta (1,1)) and the total number of subjects with DLTs and DLT-evaluable subjects for the current dose. A dose escalation/stay/de-escalation decision that corresponds to the subinterval with the highest unit probability mass will be selected. A minimum of 3 DLT-evaluable subjects will be enrolled to a dose level and evaluated for DLT before a dose escalation/stay/de-escalation decision can be made unless unacceptable toxicity is observed prior to the enrollment of 3 subjects e.g., two subjects experience DLT before the third subject enrolls. A dose level will be considered unsafe, with unacceptable toxicity and no additional subjects enrolled at that dose level and above, if it has an estimated 95% or more probability of exceeding the target DLT rate of 30%. The maximum number of subjects evaluated for DLT for each dose level will be 12 subjects (about 4 cohorts of 3 subjects) if the dose escalation decision is to stay at the current dose from the first 3 cohorts. Based on the above design, the dose escalation decision rules for each dose level are:

- Dose escalate if the observed DLT rate < 25%;
- Stay at the current dose if the observed DLT rate between 25%-33%;
- Dose de-escalate if the observed DLT rate > 33%;

See [Table 12](#) for dose escalation decision rules based on the total number of subjects evaluable for DLT and the number of DLTs observed.

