Table 12 SL-172154 Dose Escalation Decision Rules for Each Dose Level Based on mTPI-2

Number of DLTs	Number of Subjects									
	3	4	5	6	7	8	9	10	11	12
0	E	E	E	E	E	E	E	E	E	E
1	S	S	E	E	E	E	E	E	E	E
2	D	D	D	S	S	S	E	E	E	E
3	DU	DU	D	D	D	S	S	S	S	S
4	.	DU	DU	DU	D	D	D	D	D	S

5	.	.	DU	DU	DU	DU	DU	D	D	D
6	.	.	.	DU	DU	DU	DU	DU	DU	D
7	DU	DU	DU	DU	DU	DU
8	DU	DU	DU	DU	DU
E = escalate to the next higher dose level						S = stay at the current dose level				
D = de-escalate to the next lower dose level						DU = de-escalate to the next lower dose level and current dose level will never be used again due to unacceptable toxicity				

Note: For each dose level, a minimum of 3 evaluable subjects will be enrolled and evaluated before a dose escalation/stay/de-escalation decision can be made unless unacceptable toxicity is observed prior to the enrollment of 3 subjects e.g., two subjects experience DLT before the third subject enrolls.

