8.2 Maximum Tolerated Dose Evaluation

The MTD evaluation will be based on the DLT Evaluable Population. The number and percentage of subjects with DLT will be presented by dose level for the dose escalation cohorts. The MTD level will be indicated in the summary.

The MTD will be estimated using isotonic regression (based on the DLTs observed in the DLT evaluable subjects). A MAD will be reported if the DLT rate never reaches $\geq 25\%$. Otherwise, an MTD will be reported. Isotonic regression is a way to estimate the MTD under the assumption that toxicity increases with dose. When using isotonic regression, the first step is to identify the doses where the dose-toxicity monotonicity assumption is violated. The DLT estimate is then adjusted for the violators such that the final estimate of the DLT rate increase with the dose. The target DLT rate is then used to select the MTD. For example, suppose that when the trial is completed, the observed DLT rates [<# subjects who experienced DLT]/[# evaluable subjects] at four dose levels are (0/3, 1/3, 0/3, 4/15). In this example the observed DLT rate at Dose Level 2 (i.e., 1/3=33%) is higher than the observed DLT rate at Dose Level 3 (i.e., 0/3=0%). To adjust for this violation, the DLT estimates are replaced with their average, i.e., $(1/3+0/3)/2=1/6$, resulting in the isotonic regression DLT estimates $(0/3, 1/6, 1/6, 4/15) = (0\%, 16.7\%, 16.7\%, 26.7\%)$, which monotonically increases with the dose level. Based on this isotonic estimate, assuming that the trial goal is to find the dose with the DLT rate of 30%, Dose Level 4 will be selected as the MTD. If there are no violators of the dose-toxicity monotonicity assumption, isotonic regression directly uses the observed DLT rates as the final estimates for MTD selection.

In the case of dose levels with estimated toxicity of equal distance (tied dose levels) from the target toxicity of 30%, the following approach will be used: among all tied dose levels the highest dose level with target toxicity $\leq 30\%$ will be selected, unless all tied dose levels have estimated toxicity $> 30\%$, in which case the lowest dose level will be selected.

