11. CHANGE FROM PROTOCOL-SPECIFIED ANALYSES

There are no changes from the protocol-specified analyses.

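### The protocol's MTD rule can name a dose level the trial has already eliminated for toxicity, and the SAP states a different rule

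*Protocol*

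**What the plan says.** Protocol 9.1.1 sets a "target DLT rate of 30% for the MTD" and eliminates a level once the posterior probability that its DLT rate exceeds 30% reaches 95%. Enrolment then stops at that level and above. Table 12 codes such cells DU, and its legend says the "current dose level will never be used again due to unacceptable toxicity".

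Protocol 9.2.4 estimates the MTD by isotonic regression. The MTD is the dose whose estimate is "closest to the target DLT rate of 30% among all dose with the isotonic estimate of DLT rate" at or above 25%. A MAD is reported only if every level is below 25%; in all other cases an MTD is reported. For ties on both sides of 30%, "then select the higher dose among the tied doses".

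SAP 8.2 uses 25% to decide between reporting a MAD and an MTD. After the isotonic adjustment it says only: "The target DLT rate is then used to select the MTD". For ties it takes, "among all tied dose levels the highest dose level with target toxicity" at or below 30%, or the lowest level if all tied levels lie above 30%. SAP 11 states: "There are no changes from the protocol-specified analyses".

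Neither document removes eliminated levels from the MTD estimate.

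**The concern.** The 25% floor acts in the wrong direction. It disqualifies the levels that were tolerated and leaves eligible the level that was not. The better the lower dose looks, the more certain it is that the toxic dose is named. An estimator of the maximum tolerated dose should not be able to return a level that the same protocol forbids using again.

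The second problem is that two governing documents give different estimators for one quantity. MTD or MAD in each combination is listed as a primary outcome measure (Protocol 2, SAP 2), and DLT results feed the choice of RP2D. If the rules diverge on the observed data, someone must choose between them after seeing the DLTs.

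**Working it through.** **Inputs.** Target 30%, Beta(1,1) prior, 95% elimination threshold and at most 12 DLT-evaluable subjects per level (Protocol 9.1.1). Levels 1.0, 3.0 and 6.0 mg/kg, starting at 3.0 (Protocol Tables 1 and 2). About 12 escalation subjects per regimen (Protocol 9.1.4).

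**Reproducing the plan's figures.** SAP 8.2 gives the example 0/3, 1/3, 0/3, 4/15. Pooling levels 2 and 3 gives (1+0)/(3+3) = 16.7%, so the estimates are 0%, 16.7%, 16.7% and 26.7%. Level 4 is 3.3 points from 30% and is the MTD under both rules, so this example cannot reveal the difference. Regenerating the mTPI-2 table matches 75 of 75 cells in the SAP and 74 of 75 in the protocol. The exception, 3 DLTs in 8 subjects (S in the protocol, D in the SAP and on calculation), does not bear on this point. All DU cells match.

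**Elimination probabilities.** The posterior after x DLTs in n is Beta(1+x, 1+n−x).
- 3/3: Beta(4,1), P(p>0.30) = 1 − 0.3⁴ = 0.992, DU
- 4/6: Beta(5,3), 0.971, DU
- 5/9: Beta(6,5), 0.953, DU
- 3/6: Beta(4,4), 0.874, not eliminated (D)

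**Applying both rules.** Distances are in percentage points from 30%, lower level first.

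| 3.0 mg/kg | 6.0 mg/kg | Isotonic estimates | Distances | Protocol MTD | SAP MTD |
|---|---|---|---|---|---|
| 0/3 | 3/3 (DU) | 0%, 100% | 30, 70 | 6.0 | 3.0 |
| 1/6 | 3/3 (DU) | 16.7%, 100% | 13.3, 70 | 6.0 | 3.0 |
| 1/6 | 4/6 (DU) | 16.7%, 66.7% | 13.3, 36.7 | 6.0 | 3.0 |
| 1/6 | 3/6 (D) | 16.7%, 50% | 13.3, 20 | 6.0 | 3.0 |
| 0/3 | 5/9 (DU) | 0%, 55.6% | 30, 25.6 | 6.0 | 6.0 |

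In every row only 6.0 mg/kg passes the 25% floor. In the first three rows the protocol names an eliminated level and the SAP does not. The fourth shows disagreement without elimination. In the fifth both rules name an eliminated level. If 3.0 and 1.0 mg/kg both have 3/3, every tried level is DU and both documents still require an MTD.

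**Ties.** Estimates of 20% (1/5) and 40% (2/5) are both 10 points from 30%. The SAP takes the lower level. The protocol's floor removes the 20% level and leaves the 40% one.

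**How often.** Trial paths were enumerated exactly under these assumptions: cohorts of 3, start at 3.0 mg/kg, at most 12 per level, and stop when told to escalate with no level available and at least 6 treated. Each cell gives the result capped at 12 subjects per regimen, then with no overall cap. The 5/10/20% row is available only as a range.

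| True DLT rate at 1.0/3.0/6.0 | Protocol names an eliminated level | SAP does so | Rules disagree |
|---|---|---|---|
| 2/5/15% | 0.8% / 1.1% | 0.0% / 0.2% | 2.3% / 1.0% |
| 5/10/20% | 2–3% | – | 3–7% |
| 5/10/30% | 7.2% / 12.1% | 0.5% / 1.7% | 16.1% / 12.4% |
| 5/20/40% | 14.5% / 23.3% | 1.3% / 2.0% | 30.6% / 26.0% |
| 10/30/50% | 23.0% / 32.1% | 2.6% / 2.9% | 40.5% / 34.3% |
| 5/10/50% | 31.1% / 51.3% | 1.7% / 6.1% | 46.3% / 49.5% |

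**The case against.** The strongest reply is that this is a reporting label. Escalation follows Table 12, DU stops enrolment at that level and above, and the expansion dose and RP2D rest on the totality of data (Protocol 3.1, 3.4). DLT counts are tabulated by dose level, so a 3/3 would be visible. This stands: the rule does not by itself lead to dosing at an eliminated level.

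The higher frequencies also need high true DLT rates at 6.0 mg/kg. The only SL-172154 DLT data in the documents are monotherapy: none in 6 subjects at 3.0 mg/kg weekly and 1 in 5 at 10 mg/kg (Protocol 1.6.3), on a more intense schedule than this trial's. That stands as a caution on the percentages. Neither combination had been studied in humans (Protocol 1.7.1), so the true rates are unknown. The uncapped figures go beyond the planned 12 subjects per regimen. The worked outcomes need none of these assumptions.

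SAP 8.2 could be read as shorthand for the protocol rule, since it never disclaims the floor. That is possible, but its tie rule is plainly different, and if it is shorthand then the SAP inherits the defect.

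Two further points are correct. The tie conflict is minor: with at most 12 subjects per level, unpooled estimates of at least 25% cannot tie across 30%, so the protocol's straddling clause hardly operates. And the floor is not the only cause, because the SAP rule without it still fails at 0/3 and 5/9. Both documents lack an exclusion for eliminated levels.

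**Conclusion.** The concern holds. As written, the protocol can report as MTD a level with at least 95% posterior probability of exceeding the target, and six subjects are enough to produce that outcome (0/3 then 3/3). On the same data the SAP, read as written, gives the lower dose, and no departure from the protocol is declared, although Protocol 9.2 requires departures to be documented in the SAP. These conclusions follow from the text and simple arithmetic.

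Frequency depends on unknown DLT rates and on stopping conventions the documents do not give. At the planned 12 subjects per regimen, an eliminated level is named in about 1% of trials if 6.0 mg/kg is well tolerated (true rates 2/5/15%), 7% at 5/10/30%, and 31% at 5/10/50%. The harm is a wrong or disputed value for a primary outcome measure. The point should be fixed because the rule contradicts the trial's own elimination rule and the correction is nearly free.

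**What to change.** State one estimator in identical words in Protocol 9.2.4 and SAP 8.2:

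- Use the 25% threshold only to decide whether the result is labelled MTD or MAD.
- Run the closest-to-30% search over levels that were tried and are not eliminated (DU, or above a DU level).
- State that no MTD is reported if every tried level is eliminated.
- Carry one tie rule in both documents; the SAP's version is the more cautious.

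Under this rule all five tabulated outcomes give 3.0 mg/kg, including 0/3 and 5/9, where adopting the SAP text alone would not help. If the protocol is not amended, record the change in SAP 11 in place of the present statement. The cost is a paragraph in each document, with no additional subjects or data.
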